19. EXPLORATORY OUTCOMES

19.1. PARTS A AND B

The following exploratory parameters will be evaluated using ad-hoc descriptive analysis in **Parts A and B** based on ITT analysis set and PP analysis set:

- The effect of Givinostat on each single response parameter according to the clinico-haematological ELN (for PV and ET) [1] and EUMNET response criteria (for MF) [7]; note that only in case the enrolment in Part A is slow (i.e. < 5 patients enrolled in 3 months), the eligibility for this part of the study could be expanded to all patients with cMPN.
- Effects of Givinostat on PD markers.
- Effects of Givinostat on spleen size in patients with confirmed splenomegaly at baseline.
- Improvement of constitutional symptoms evaluated according to MPN-SAF QOL questionnaire [8, 9] including patients without the symptom of headache, pruritus and microvascular symptoms (i.e MPN SAF Score =0) and number and percentage of patient with symptom score from 0 to 3; from 4 to 6 and more than 7.

Document: PPD

Author: PPD

Version Number:

V2.2

Version Date:

21 March 2018

Template No: CS_TP_BS016 – Revision 3

Reference: CS_WI_BS005

Effective Date: 01May2012

Copyright © 2012 Quintiles Transnational Corp. All rights reserved.

The contents of this document are confidential and proprietary to Quintiles Transnational Corp. Unauthorized use, disclosure or reproduction is strictly prohibited.

- Reduction of the JAK2V617F allele burden, tested by quantitative RT-PCR.
- Reduction of the symptomatic treatment of pruritus in term of dosage and/or days of treatment.

The following exploratory parameters will be evaluated using ad-hoc descriptive analysis in Part B based on ITT analysis set and PP analysis set:

- The preliminary efficacy of Givinostat after 6 cycles of treatment according to the “new” ELN criteria (i.e. revised ELN response criteria) [2]. In all cases, the medical judgment of the Investigator’s is taken into account. In particular, if the Investigator’s clinical response assessment – that takes into account the overall medical judgment of the specific patient’s case - is not in agreement with the exact application of the revised clinico-haematological ELN response criteria , the Investigator’s assessment will supersede the “mathematical” application of these criteria and used for analysis into study report. Also mathematical application of ELN response criteria (not agreed by the medical site team) will be analyzed.
- The effect of Givinostat on single parameters of the “new” ELN response criteria (i.e. revised ELN response criteria) [2].

The “new” ELN response criteria [2] are detailed in the [paragraph 4.8.7](#) of the Study protocol.

Explorative endpoints will be summarised by descriptive methods based on ITT analysis set and PP analysis set. Default summary statistics and changes from baseline (*where applicable*) to each time point for all parameters will be produced.

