5.2. INTENT-TO-TREAT ANALYSIS SET (ITT)

The Intent-to-treat analysis set will include all recruited patients who receive at least one dose of study medication and from whom at least one post-baseline efficacy measurement is obtained.

Of note, patients who dropped the study due to drug-related TEAE(s) before that the post-baseline efficacy measurement is obtained (i.e. at C3D28 and/or at C6D28), will be considered in the ITT analysis set; in these cases, the post-baseline efficacy measurements (i.e. at C3D28 and/or at C6D28) will be considered as “No Response”, even if these assessments were not performed.

In addition, patients who have performed the visit when the post-baseline efficacy measurements (i.e. at C3D28 and/or at C6D28) had to be performed, but for which the following conditions will happen, will be excluded from the ITT analysis set:

- HCT > 45% or HCT ≤ 45% with phlebotomy(ies), AND
- at least 2 out of 4 assessments of the following will be not performed:
 - a) WBC count;

Document: PPD

Author: PPD

Version Number:

V2.2

Version Date:

21 March 2018

Template No: CS_TP_BS016 – Revision 3

Reference: CS_WI_BS005

Effective Date: 01May2012

Copyright © 2012 Quintiles Transnational Corp. All rights reserved.

The contents of this document are confidential and proprietary to Quintiles Transnational Corp. Unauthorized use, disclosure or reproduction is strictly prohibited.

- b) PLT count;
- c) Spleen evaluation by CT scan or MRI;
- d) Disease-related assessment by MPN-SAF.

This is due to the fact that is not possible to define a clinico-haematological response as per ELN response criteria in these cases.

All efficacy analyses will be conducted on this population and will be based on the *effective/actual* DL/daily doses of Givinostat at which each patient has been treated.

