5.5. PK ANALYSIS SET (PK)

The PK Analysis Set will consist of all SAF patients with at least 1 PK assessment.

This analysis set will be used for PK analysis.

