21. MOLECULAR ANALYSIS

Results from the molecular analysis performed during the Study will be listed, including results from pharmacodynamic (PD) markers.

The following information will be provided for JAK2^{V617F} allele burden evaluations:

- JAK2^{V617F} positivity (Yes/No);
 - Qualitative evaluation of JAK2V617F allele burden
 - Heterozygous
 - Homozygous
- Quantitative evaluation of JAK2V617F allele burden (%);
- Actual and change from baseline by visit;
- Number (n) and percentage (%) of patients with:
 - a reduction of any specific molecular abnormality to undetectable levels;

Document: PPD

Author: PPD

Version Number:

V2.2

Version Date:

21 March 2018

Template No: CS_TP_BS016 – Revision 3

Reference: CS_WI_BS005

Effective Date: 01May2012

Copyright © 2012 Quintiles Transnational Corp. All rights reserved.

The contents of this document are confidential and proprietary to Quintiles Transnational Corp. Unauthorized use, disclosure or reproduction is strictly prohibited.

- a reduction of $\geq 50\%$ from baseline value in patients with $< 50\%$ mutant allele burden at baseline;
 - a reduction of $\geq 25\%$ from baseline value in patients with $> 50\%$ mutant allele burden at baseline.
- Descriptive statistics of quantitative evaluation of JAK2^{V617F} allele burden.

Notably, approximately 4.0 mL of blood for PD markers is collected before the first Givinostat dose (pre-dose) and 12 hours after the first Givinostat dose (post-dose) at C1D1 both in **Part A** and in **Part B** for measurement of levels of molecular markers, to evaluate the PD effect of Givinostat and to identify markers predictive of clinical benefit of Givinostat (see [Appendix A](#) of the Study protocol). In addition, PD evaluations are performed also using an aliquot of the PK samples collected at time points described in the [paragraph 4.5.3.2](#) of the Study protocol. The molecular markers to be measured may include mRNA levels of JAK2, STAT5A, BclXL, PIM1, NFE2, LMO2, cMyc as well as HDAC3, STAT4, MYBL1, MEGF9, GLRX, FAM49A. The final list of PD markers to be measured will depend on ongoing scientific developments as well as availability of assays and other business considerations. For all time points an additional PD blood sample is collected as back-up sample.

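### Section 19.1 ties the PD-marker and early JAK2V617F summaries to the efficacy-based ITT and PP sets, so some valid early samples drop out of the summaries, and Section 21 names no set

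*SAP*

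**What the plan says.** Section 19.1 names "Effects of Givinostat on PD markers" and "Reduction of the JAK2V617F allele burden, tested by quantitative RT-PCR" among the exploratory parameters for Parts A and B, to be evaluated in the ITT and PP sets. It closes with the general rule "Explorative endpoints will be summarised by descriptive methods based on ITT analysis set and PP analysis set".

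The sets are defined in Section 5:

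- **ITT (5.2)** takes recruited patients "who receive at least one dose of study medication and from whom at least one post-baseline efficacy measurement is obtained". One group of early leavers is kept and scored as non-responders: "patients who dropped the study due to drug-related TEAE(s) before that the post-baseline efficacy measurement is obtained (i.e. at C3D28 and/or at C6D28"). A further rule removes patients who attended the response visit but failed the haematocrit condition and lack at least two of four other components (WBC, platelets, spleen imaging, MPN-SAF). The stated reason is that an ELN response cannot then be defined.
- **PP (5.3)** adds 14 uninterrupted daily doses and freedom from major deviations. Section 5.3.1 counts late SAE reporting, prohibited medication and compliance under 80% among the major ones.
- **PK (5.5)** has no efficacy condition: "The PK Analysis Set will consist of all SAF patients with at least 1 PK assessment".

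Section 21 describes PD blood taken before the first dose and 12 hours after it, and adds that "PD evaluations are performed also using an aliquot of the PK samples collected at time points" set out in the protocol. It lists all molecular results and summarises JAK2 burden by dose level and time point, but names no analysis set. Section 3.7 (Amendment 2, item 22) adds Part B JAK2 samples at Day 28 of Cycles 1, 2, 4 and 5.

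**The concern.** A 12-hour mRNA change, or an allele burden at the end of Cycle 1, needs no clinical response assessment to be interpretable. Under 19.1, whether it enters the summary depends on what happens to the patient by week 12 (ITT) or over the rest of treatment (PP). The reasons for exclusion (an ELN category that cannot be assigned, a late SAE form) have no bearing on the validity of the sample.

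Two things are at stake. The summaries rest on fewer patients than were measured. The selection may also not be neutral: Section 16.6 foresees patients stopping for disease-related deterioration, and such a patient leaving before Cycle 3 Day 28 is not covered by the TEAE rule. Separately, one blood sample can count in the PK tables and be absent from the PD summary. Sections 19.1 and 21 also do not agree on whether any set restriction applies to JAK2.

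**Working it through.** The plan has no figure of its own on this point, so the check sets the sampling times against the conditions for entering each set.

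| Measurement | When taken | Source |
|---|---|---|
| PD markers | Pre-dose and 12 hours after first dose, C1D1 | Section 21 |
| PD from PK aliquots | At PK time points | Section 21 |
| JAK2 burden, Part B (early samples) | C1D28, C2D28 | Section 3.7 |
| ELN response | C3D28 (week 12), C6D28 (week 24) | Section 16.3 |

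The outcome for a patient with a valid early sample is then:

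| Patient | ITT summary | PP summary | Listings (Section 21) |
|---|---|---|---|
| Leaves before C3D28 for a drug-related TEAE | In | In only if the PP conditions are met | In |
| Leaves before C3D28 for another reason, no efficacy measurement | Out | Out | In |
| Attends the response visit, haematocrit condition failed, at least 2 of 4 components missing | Out | Out | In |
| Has a response assessment, later major deviation (e.g. late SAE report) | In | Out | In |

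All the tabulated Day 1, C1D28 and C2D28 samples precede C3D28. In rows two to four the exclusion therefore rests on something later than the sample. ITT asks for only one efficacy measurement, so a C3D28 assessment meets the basic condition at week 12. A reach to the end of treatment comes mainly from PP.

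**Size.** The SAP gives no drop-out or exclusion rate, so these figures are assumptions:

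- Part B, 1 to 4 of 28 excluded: 1/28 = 3.6% to 4/28 = 14.3%.
- Part B Stage 1, 1 to 4 of 12 excluded: 1/12 = 8.3% to 4/12 = 33.3%.
- Part A, one excluded: 1/3 = 33.3% of a three-patient group, 1/6 = 16.7% of a six-patient group. Table 1.1 labels DL1 and DL1 expanded as separate groups of three.
- As a rate, 5% to 20% of 28 is 0.05 × 28 = 1.4 to 0.20 × 28 = 5.6 patients.

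**Design figures.** The Part B design in Section 3.5 was recomputed by exact binomial sums (continue with at least 7 of 12 responders, reject the null with at least 18 of 28). Early termination is 0.6128, expected size 18.20, type I error 0.0815 and power 0.9017. The plan states 0.613, 18.2, 0.081 and 0.902. None of these depends on the set used for PD or JAK2.

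**The case against.** The best defence is that one efficacy set for all exploratory endpoints is a conventional choice, and that little is lost here. Much of this stands:

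- The TEAE rule in 5.2 keeps the early drop-outs most likely to be related to drug effect, so ITT losses are confined to the second and third patient types in the table.
- PP is a robustness repeat (5.3). Its exclusions take nothing from the ITT summary.
- Section 7.5 treats these analyses as hypothesis-generating.

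A reader might infer that the samples are lost, or that exposure and PD effect from one blood draw can no longer be matched. The documents do not support either. Section 21 lists molecular results by patient, Sections 18.1 and 18.2 tabulate individual concentrations, and Section 6.3 puts all scheduled, unscheduled and early-discontinuation data into listings. Matching at patient level remains possible, and no PK-PD table is planned that differing denominators would break.

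A reader might also put the cost as a loss of precision. With assumed losses of one in three or 4 in 28, a standard error would rise by 22% (√(3/2) = 1.225) or 8% (√(28/24) = 1.080). But the plan reports no standard error or interval for these endpoints: Section 21 gives n, mean, SD, CV, median, minimum and maximum.

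Finally, if an efficacy measurement were read to include earlier haematology, ITT losses would shrink. Section 5.2 ties it to C3D28 and C6D28, however, and the missing-component rule would remain. The defence gives no reason why an undefined ELN category should remove a Day 1 PD pair.

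**Conclusion.** The point holds in a narrow form. Section 19.1 states a rule that leaves some valid early PD and JAK2 results out of the summaries, though not out of the listings, for reasons unrelated to those results. Section 21 summarises JAK2 without saying which set applies, so the two sections need aligning.

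How many patients are affected is unknown, and the direction of any selection effect cannot be determined from the document. Bias is possible but not shown. The endpoints are exploratory and descriptive, and the primary analysis and the Simon decision are untouched. This is a free improvement, not a flaw in the trial's conclusions. It rests on reading the ITT efficacy measurement as the C3D28/C6D28 response assessment, as 5.2 indicates.

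**What to change.** In Sections 19.1 and 21, state that PD markers and JAK2V617F burden are summarised by visit in all SAF patients with a baseline and at least one post-dose result for that marker. Such a set is SAF-based like the PK set but not identical to it, since PK needs only one assessment and a change from baseline needs two results. The plan already takes this route elsewhere: Section 20.4 reports spleen results in the SAF set although spleen size is also listed in 19.1.

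Drop the PP repeat for the Day 1 PD effect, and use ITT only if markers are related to clinical response.

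The cost is one sentence in the SAP and one population flag in the programs. No new data and no design change are needed.

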20. OTHER SAFETY OUTCOMES

All patients who receive at least one dose will be included in the safety evaluation.

Safety data including laboratory evaluations, physical exams, ECG monitoring and vital signs assessments will be summarised at each time point.

Descriptive statistics (arithmetic mean, standard deviation, median, minimum and maximum) will be calculated for quantitative safety data as well as for the difference from baseline, *if applicable*. Frequency counts will be compiled for classification of qualitative safety data.

In addition, a shift table describing out of normal range shifts (low/normal/high values) will be provided for clinical laboratory results.

A normal-abnormal shift table will also be presented for physical exam and ECG results.

20.1. LABORATORY EVALUATIONS.

Results from the local laboratories will be included in the reporting of this study for Haematology,

Document PPD

Author: PPD

Version Number:

V2.2

Version Date:

21 March 2018

Template No: CS_TP_BS016 – Revision 3

Reference: CS_WI_BS005

Effective Date: 01May2012

Copyright © 2012 Quintiles Transnational Corp. All rights reserved.

The contents of this document are confidential and proprietary to Quintiles Transnational Corp. Unauthorized use, disclosure or reproduction is strictly prohibited.

Blood Chemistry and Urinalysis.

A list of laboratory assessments to be included in the outputs is included in the [paragraph 4.7.1](#) of the Study protocol.

Outputs will be based on the SAF analysis set, presented by DL (for **Part A only**), and will use the International System (SI) Units.

The following summaries will be provided for Haematology, Blood Chemistry, Urinalysis laboratory data by DL (for **Part A only**):

- Actual and change from baseline by visit (for quantitative measurements);
- Shift from baseline according to normal range criteria (for categorical measurements);
- Presence/absence, with number (n) and percentage (%), where applicable (i.e. Glucose and Protein, for Urinalysis test).
- Listing of laboratory data by Study Part and patient ID;
- Listing of patients with clinically significant abnormal values, as reported in electronic CRF based on Investigator’s judgment;
- Listing of patients with markedly significant abnormal values (e.g. grade 3 thrombocytopenia as per CTCAE version 4.03).

20.2. LABORATORY SPECIFIC DEVIATIONS

To convert from each local laboratory conventional unit to the SI unit, values will be multiplied by the conversion factor:

Component	Conventional Unit	Conversion Factor	SI Unit
Haematology			
Haematocrit	%	0.01	Proportion of 1.0
Haemoglobin	g/dL	10	g/L
RB count	$\times 10^6/\mu\text{L}$	1	$\times 10^{12}/\text{L}$

Document: PPD

Author: PPD

Version Number:

V2.2

Version Date:

21 March 2018

Template No: CS_TP_BS016 – Revision 3

Reference: CS_WI_BS005

Effective Date: 01May2012

Copyright © 2012 Quintiles Transnational Corp. All rights reserved.

The contents of this document are confidential and proprietary to Quintiles Transnational Corp. Unauthorized use, disclosure or reproduction is strictly prohibited.

Platelets	x 10 ³ /μL	1	x 10 ⁹ /L
WB count	x 10 ³ /μL	1	x 10 ⁹ /L
Basophils	x 10 ³ /μL	1	x 10 ⁹ /L
Eosinophils	x 10 ³ /μL	1	x 10 ⁹ /L
Lymphocytes	x 10 ³ /μL	1	x 10 ⁹ /L
Monocytes	x 10 ³ /μL	1	x 10 ⁹ /L
Neutrophils	x 10 ³ /μL	1	x 10 ⁹ /L
Mean Corpuscular Volume	fL	1	μm ³
Mean Corpuscular Haemoglobin	Pg	0.062	fmol
Mean Corpuscular Haemoglobin Concentration	g/dL	10	g/L
Blood Chemistry			
Sodium	mEq/L	1.0	mmol/L
Potassium	mEq/L	1.0	mmol/L
Calcium	mg/dL mEq/L	0.25 0.50	mmol/L
Chloride	mEq/L	1	mmol/L
Magnesium	mg/dL	0.4114	mmol/L
Albumin	g/dL	10	g/L
Blood Glucose	mg/dL	0.0555	mmol/L
BUN	mg/dL	0.357	mmol/L
Urea	mg/dL	0.357	mmol/L

Document: PPD

Author: PPD

Version Number:

V2.2

Version Date:

21 March 2018

Template No: CS_TP_BS016 – Revision 3

Reference: CS_WI_BS005

Effective Date: 01May2012

Copyright © 2012 Quintiles Transnational Corp. All rights reserved.

The contents of this document are confidential and proprietary to Quintiles Transnational Corp. Unauthorized use, disclosure or reproduction is strictly prohibited.

Creatinine	mg/dL	88.4	μmol/L
Alanine aminotransferase (ALT)	U/L	1	U/L
Aspartate aminotransferase (AST)	U/L	1	U/L
Alkaline phosphatase	U/L	1	U/L
Total Bilirubin	mg/dL	17.104	μmol/L
Lactate Dehydrogenase	U/L	1	U/L
Urinalysis			
pH	(unitless)		
Specific Gravity	(unitless)		
Glucose	mg/dL	0.0555	mmol/L
Protein	g/dL	10.0	g/L

LABORATORY REFERENCE RANGES AND MARKEDLY ABNORMAL CRITERIA

Quantitative laboratory measurements will be compared with the relevant laboratory reference ranges in local units and categorized as:

- Low: Below the lower limit of the laboratory reference range.
- Normal: Within the laboratory reference range (upper and lower limit included).
- High: Above the upper limit of the laboratory reference range.

Potentially clinically significant laboratory values will be summarised by laboratory variable. Platelets values will be evaluated as a potentially clinically significant low value at any time during the study, and will be presented by visit.

Document: PPD

Author: PPD

Version Number:
Version Date:

V2.2
21 March 2018

Template No: CS_TP_BS016 – Revision 3
Effective Date: 01May2012

Reference: CS_WI_BS005

The Platelets potentially clinically significant low value is defined as follows:

- Platelets count $< 150 \times 10^9/L$ but $> 75 \times 10^9/L$ (i.e. grade 1 thrombocytopenia as per CTCAE version 4.03);
- Platelets count $< 75 \times 10^9/L$ but $> 50 \times 10^9/L$ (i.e. grade 2 thrombocytopenia as per CTCAE version 4.03);
- Platelets count $< 50 \times 10^9/L$ but $> 20 \times 10^9/L$ (i.e. grade 3 thrombocytopenia as per CTCAE version 4.03);
- Platelets count $< 25 \times 10^9/L$ (i.e. grade 4 thrombocytopenia as per CTCAE version 4.03).

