The dose modifications rules to be applied in **Part B** have been updated based on the data related to the patients enrolled in **Part A** of this Study and to the results obtained in previous studies with Givinostat on cMPN. The objective of the updated Givinostat dose adjustments rules are to optimize the response for each individual patient, avoiding specific drug-related toxicities. Therefore, dose reductions or interruptions are mandated for specific toxicities and dose increases after an initial dose reduction are allowed in case of inadequate efficacy at the reduced dosage in absence of specific toxicities.

Notably, the same dose modification criteria could be followed by patients initially dosed at lower dose levels in **Part A** that, after the definition of MTD, could be allowed to escalate their Givinostat dose at MTD for the remainder part of the study (**Part A**) at the discretion of the Investigator and Sponsor.

16. Addition of the strength of 75 mg.
17. Addition of PD evaluations, performed using an aliquot of the PK samples.
18. Clarification of the calculation of eGFR (i.e. a derived biochemical parameter) in accordance with the Mayo Clinic Quadratic Equation, as agreed with the German Regulatory Authority.
19. To allow the evaluation of Urea (in spite of BUN) in accordance with the site-specific clinical practice.

Document: PPD

Author: PPD

Version Number:

V2.2

Version Date:

21 March 2018

Template No: CS_TP_BS016 – Revision 3

Reference: CS_WI_BS005

Effective Date: 01May2012

Copyright © 2012 Quintiles Transnational Corp. All rights reserved.

The contents of this document are confidential and proprietary to Quintiles Transnational Corp. Unauthorized use, disclosure or reproduction is strictly prohibited.

20. Addition of the recommendation to perform two additional ECG evaluations over a brief period (i.e. 5 minutes between each recording), if the first ECG evaluation demonstrates a prolonged QTc interval (i.e. a QTc interval \geq 450 msec).
21. Clarification of the fact that in **Part B** it is recommended that patients should be told to arrive after an overnight fast of at least 8 hours at all Study visits that requested a blood test.
22. Addition of the collection of a blood sample for the quantitative RT-PCR evaluation of JAK2^{V617F} mutational status on peripheral blood granulocyte at the following Study visits of **Part B**: Day 28 of Cycles 1, 2, 4 and 5.

CHANGES IN THE PLANNED ANALYSIS

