16.8. LABORATORY EVALUATIONS

The following laboratory examinations (haematology, blood chemistry and urinalysis) are performed at each investigational unit by a local laboratory co-operating with the Investigator following its own procedures:

- **Haematology:** RBC count, HCT, Hb, MCV, MCH, MCHC, WBC count (full and differential), PLT count;
- **Blood chemistry:** ALT/SGPT, AST/SGOT, ALP, total bilirubin, LDH, creatinine, BUN or Urea (as per site-specific clinical practice), glucose, Na, K, Ca, Cl, Mg, albumin, eGFR determination (according to the Mayo Clinic Quadratic Equation);
- **Urinalysis:** pH, specific gravity, protein, glucose.

The required amount of blood and urine are collected at each visit as scheduled above. Timing information are summarised in the Study flow-chart ([Appendix A](#) of the Study protocol) and detailed in the [paragraph 4.5.4](#) of the Study protocol.

All results of laboratory examinations are entered into the appropriate electronic CRF sections.

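### SAP section 20.2 gives urea the BUN conversion factor (0.357 instead of 0.1665), so urea reported in mg/dL would appear 2.14 times too high in the SI outputs

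*SAP*

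**What the plan says.** SAP section 20.2 sets one rule for all laboratory data: "To convert from each local laboratory conventional unit to the SI unit, values will be multiplied by the conversion factor". The table below it lists the two related analytes as separate rows with one shared factor: "BUN mg/dL 0.357 mmol/L" and "Urea mg/dL 0.357 mmol/L".

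Elsewhere the SAP treats BUN and urea as different measurements. Section 10 lists them as two blood chemistry parameters. Section 16.8 has each site's local laboratory measure "BUN or Urea (as per site-specific clinical practice"). Section 3.7 gives the origin, item 19 of Amendment 2: "To allow the evaluation of Urea (in spite of BUN) in accordance with the site-specific clinical practice". The same section counts that item among those that affect the planned analyses.

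On units, section 20.1 says that laboratory outputs "will use the International System (SI) Units". These outputs include actual values and changes from baseline by visit, and listings. Classification against normal ranges is handled differently. Section 20.2 says: "Quantitative laboratory measurements will be compared with the relevant laboratory reference ranges in local units and categorized as" low, normal or high.

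**The concern.** A mg/dL of urea and a mg/dL of urea nitrogen are different molar amounts of the same molecule, so one factor cannot serve both rows. Nothing in the SAP says that the urea row is to be read as urea nitrogen. If it were, a second row would serve no purpose.

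What is at stake is the accuracy of the urea figures in the safety tables and listings. A site reporting urea in mg/dL would have its values inflated, while a site already reporting mmol/L would need no conversion and would not. A summary that pools the two would mix two scales. Groups are small (three or six patients at DL1 in Part A, 28 in Part B), so a few such patients could shift a mean or set a maximum. A reader of the SI tables would have no way to see the cause.

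**Working it through.** **Inputs.** The factors, units and multiplication rule come from SAP section 20.2. The molar masses are not in the SAP. They follow from standard atomic masses (C 12.011, H 1.008, N 14.007, O 15.999), which are physical constants.

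- Urea, CO(NH2)2: 12.011 + 4 × 1.008 + 2 × 14.007 + 15.999 = 60.056 g/mol.
- Nitrogen in one urea molecule: 2 × 14.007 = 28.014 g/mol.

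**Formula.** Factor from mg/dL to mmol/L = 10 / molar mass. For µmol/L, use 10,000 / molar mass.

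**Step 1: does the formula reproduce the plan's other factors?**

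| Analyte | Computed | SAP table |
|---|---|---|
| Glucose | 10/180.156 = 0.0555 | 0.0555 |
| Calcium | 10/40.078 = 0.2495 | 0.25 |
| Magnesium | 10/24.305 = 0.4114 | 0.4114 |
| Creatinine | 10,000/113.12 = 88.40 | 88.4 |
| Total bilirubin | 10,000/584.66 = 17.104 | 17.104 |
| BUN | 10/28.014 = 0.3570 | 0.357 |

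It does, so the method is the one behind the table.

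**Step 2: the urea row.** 10/60.056 = 0.1665, against 0.357 in the SAP. The row does not reproduce. Its value is the BUN factor.

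**Step 3: size.** 0.357 / 0.1665 = 2.144, a 2.14-fold inflation.

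| Urea, mg/dL | × 0.357 (SAP), mmol/L | × 0.1665, mmol/L | Excess, mmol/L |
|---|---|---|---|
| 20 | 7.1 | 3.3 | 3.8 |
| 30 | 10.7 | 5.0 | 5.7 |
| 40 | 14.3 | 6.7 | 7.6 |
| 50 | 17.9 | 8.3 | 9.5 |

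**Step 4: which outputs move?** Take a patient who goes from 30 to 40 mg/dL. The absolute change is 10 × 0.357 = 3.6 mmol/L under the SAP and 10 × 0.1665 = 1.7 mmol/L with the urea factor. The percentage change, by the formula in section 6.6, is 10/30 = 33.3% either way, because the factor cancels. Means, standard deviations, minima and maxima of levels and absolute changes scale by 2.14 when all contributing values were converted. They scale by less, in an uncontrolled way, when converted and unconverted values are pooled. The low/normal/high class is set in local units before conversion and does not move.

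**The case against.** The arithmetic is hard to dispute. The case on the other side concerns reach, and most of it stands.

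- **No decision uses the converted value.** Urea is one of 16 chemistry parameters in section 10, and it enters descriptive summaries and listings only. Adverse event grades are those the investigator assigns, and DLTs are taken from an eCRF question (section 17.1). The only numeric laboratory limits in section 20.2 are for platelets. The response criteria in section 16.3 use haematocrit, platelets, white cells, spleen and symptoms. The MTD, the Simon decision and the efficacy results are untouched.
- **No false trend.** A reader might infer that the tables would suggest drug-induced renal impairment. The documents do not support that. The same multiplier applies to a patient's baseline and to every later value, so levels read high before the first dose as well. A real absolute change would be magnified, but none would be created. Creatinine, whose factor is right, and eGFR are reported separately.
- **Extent unknown.** A reader might also infer from Amendment 2 that the wrong factor is bound to be applied. The SAP only permits urea where that is site practice. The error bites only where a site reports urea and does so in mg/dL, and the SAP does not say whether that is none, some or many.
- **Labelling.** A site could enter urea nitrogen under the name urea, in which case 0.357 would be right for it. Nothing in the SAP suggests this, and the separate BUN row points the other way. It is still a reason to check labels before converting.

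None of this makes the row correct. It limits the consequence.

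**Conclusion.** The urea factor in section 20.2 is wrong as written, and no other part of the SAP corrects it. Where it is applied to urea in mg/dL, SI levels, absolute changes, their summary statistics and listings come out 2.14 times too high, at baseline and after dosing alike, and are not comparable with urea from sites reporting mmol/L. The size rests on one assumption: that values entered as urea in mg/dL are whole-molecule urea.

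Severity is moderate. The plan prespecifies a wrong constant for a safety table, but the effect is confined to one descriptive parameter at an unstated number of sites.

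**What to change.** In the section 20.2 table, change the urea factor to 0.1665 and leave BUN at 0.357. Before converting, confirm for each site whether the analyte is urea or urea nitrogen and in which unit it was reported. If a site's value is really urea nitrogen, the new factor would understate it by the same 2.14-fold. Then produce the urea summaries and listings with the corrected factor, or re-run them if they already exist. The SAP does not show which applies.

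The cost is one number in the SAP and in the program, a short check of site laboratory units, and the urea outputs. If no site reported urea in mg/dL, only the table entry changes.
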